				0 = No, else if subject attended at least one post- operative visit 6 weeks or after and complication(s) of interest specified above are reported as "Not Evident" across all attended post-operative visits. Subjects with missing responses are included as long as the subject has at least one "Not Evident" response (assuming low missing response rate among attended visits).
				
 
. = Missing, otherwise
 
*Note: Prior to and upon database lock, any new or worsening urgency urinary incontinence events identified by the MedDRA coded preferred term "urgency urinary incontinence" ) collected ONLY on the AE log with start date after surgery and not reported on any of the complications tables will be assessed, and if any, included in this definition at the discretion of the principal investigator.
 

Indicator of new or worsening fecal incontinence (FI)	CRF-12, CRF-13, CRF-96	Binary	surgery through 3 years	Through the timepoint of follow-up, based on the Adverse Event Log (CRF-96) or specific complications as reported on the masked post-operative CRF-12 and coordinator follow-up CRF-13 collected at 6-weeks and in 6-month intervals through 3 years, the indicator is defined as follows:
				1 = Yes, if new or worsening FI is reported as evident (i.e. response of "AE", "SAE") on any of the complication tables as described above or "Fecal incontinence" in the term reported in the AE log.

				0 = No, else if subject attended at least one post- operative visit 6 weeks or after and complication(s) of interest specified above are reported as "Not Evident" across all attended post-operative visits. Subjects with missing responses are included as long as the subject has at least one "Not Evident" response (assuming low missing response rate among attended visits).
				. = Missing, otherwise
				*Note: Prior to and upon database lock, any new or worsening fecal incontinence events identified by the MedDRA coded preferred term "fecal incontinence" ) with start date after surgery collected ONLY on the AE log and not reported on any of the complications tables will be assessed, and if any, included in this definition at the discretion of the principal investigator.

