Indicator of sexually active denovo dyspareunia**	PISQ-IR	Binary	surgery through 3 years	At each timepoint among women who were sexually active (PISQ-IR Q1: 1=yes) at baseline and at the timepoint's corresponding attended post-operative visit, based on the response to the PISQ-IR question Q11 "How often do you feel pain during sexual intercourse? " at baseline and the timepoint's corresponding attended post-operative visit, the indicator is defined as follows:
				1 = Yes, if a response of 1=never or 2=rarely is reported at baseline and a response of 3=sometimes, 4=usually, or 5=always is

				reported at the timepoint's corresponding attended post-operative visit 0 = No, else if there is a non-missing response reported at baseline and at the timepoint's corresponding attended post-operative visit . = Missing, otherwise
Indicator of not sexually active denovo dyspareunia**	PISQ-IR	Binary	surgery through 3 years	At each timepoint among women who were not sexually active (PISQ-IR Q1: 2=no) at baseline and at the timepoint's corresponding attended post-operative visit, based on the response to the PISQ-IR question Q2e asking if pain is a reason for not being sexually active at baseline and the timepoint's corresponding attended post-operative visit, the indicator is defined as follows:
				1 = Yes, if a response of 3=somewhat disagree or 4=strongly disagree is reported at baseline and a response of 1=strongly agree or 2=somewhat agree is reported at the timepoint's corresponding attended post- operative visit
				0 = No, else if there is a non-missing response reported at baseline and at the timepoint's corresponding attended post-operative visit
				. = Missing, otherwise
Indicator of dyspareunia	CRF-13, CRF-96	Binary	surgery through 3 years	Through the timepoint of follow-up, based on the Adverse Event Log (CRF-96) or specific complications as reported on the coordinator follow-up CRF-13 collected in 6-month intervals through 3 years, the indicator is defined as follows:

				1 = Yes, if denovo dyspareunia, worsening dyspareunia, or dyspareunia preventing intercourse is reported as evident (i.e. response of "AE", "SAE") on any of the complication tables as described above or "Dyspareunia" in the term reported in the AE log.

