				0 = No, else if subject attended at least one post- operative visit 6 months or after and complication(s) of interest specified above are reported as "Not Evident" across all attended post-operative visits. Subjects with missing responses are included as long as the subject has at least one "Not Evident" response (assuming low missing response rate among attended visits).
				
 
. = Missing, otherwise
 
*Note: Prior to and upon database lock, any dyspareunia events identified by the MedDRA coded preferred term "dyspareunia" ) with start date after surgery collected ONLY on the AE log and not reported on any of the complications tables will be assessed, and if any, included in this definition at the discretion of the principal investigator.
 

Indicator of new or worsening voiding dysfunction	CRF-12, CRF-13, CRF-96	Binary	surgery through 3 years	Through the timepoint of follow-up, based on the Adverse Event Log (CRF-96) or specific complications as reported on the masked post-operative CRF-12 and coordinator follow-up CRF-13 collected at 6-weeks and

in 6-month intervals through 3 years, the indicat defined as follows:	or is
1 = Yes, if new or worsening difficulty em bladder is reported as evident (i.e. of "AE", "SAE") on any of the com tables as described above or "Urina Retention" in the term reported in t log Masked review identified free other specify complication fields co "incomplete bladder emptying", retention " (case insensitive) on any complication tables as described ab CRF-12 collected at 6-weeks and in intervals through 3 years and 1-yea thereafter.	response nplication ary the AE text ontaining "urinary y of the pove or on n 6-month
0 = No, else if subject attended at least one p operative visit 6 weeks or after and complication(s) of interest specified are reported as "Not Evident" across attended post-operative visits. Subj missing responses are included as le subject has at least one "Not Eviden response (assuming low missing response (assuming low missing response).	d above ss all ects with ong as the nt"
. = Missing, otherwise	
*Note: Prior to and upon database lock, any void dysfunction events identified by the MedDRA co preferred term "urinary retention" collected ONI AE log with start date after surgery and not repo any of the complications tables will be assessed,	oded LY on the orted on

				any, included in this definition at the discretion of the principal investigator.

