## 9.5 Secondary Efficacy Analysis Methods

### **9.5.1** Secondary Efficacy Outcomes

All secondary anatomical and functional efficacy outcomes are collected longitudinally across the study. All analyses for secondary outcomes are considered to be descriptive rather than inferential, so p-values will be interpreted as measures of evidence of descriptive differences in the treatment arms, not formal inferences.

For all secondary outcomes, point estimates and 95% confidence intervals for pairwise comparisons between each of the mesh repairs versus the native tissue repair as well as between the two mesh repairs will be obtained along with a p-value for the overall test assessing if any of the treatment effects are different. Treatment groups will be compared in the MITT population for all secondary efficacy outcomes.

Unless otherwise specified, all other secondary efficacy outcomes collected across multiple visits, analyses will include data only collected through 3 years (visits occurring after 3 years are excluded) using appropriate adjusted repeated measures models that account for subject correlations across visits. If the data corresponding to a secondary efficacy outcome is also collected at baseline prior to surgical intervention, these outcomes will be analyzed as change from baseline. Models will be adjusted for randomized surgical intervention, time in months as intended by the visit schedule, intervention by time interaction, baseline value, pooled site and age category consistent with study randomization design.

Treatment groups will be compared for any secondary efficacy outcomes evaluated in an aggregate fashion (e.g. proportion of participants with an event occurrence through 3 years), using a chi-square test or Fishers exact test for rare events. Additional details are provided in the specific sections below.

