Indicator of vaginal shortening after 12 weeks	CRF-10, AE log	Binary	after 12 weeks through last visit	Through the timepoint of follow-up, based on the systematic collection of open-ended adverse events as reported on the AE log with an onset start date 12 weeks after the date of surgical intervention and based on the specific complications as reported on the evaluator (blinded) follow-up CRF-10 collected at 6-weeks and in 6-month intervals through 5 years, the indicator is defined as follows:
				1 = Yes, if vaginal shortening is reported as evident (i.e. response of "AE", "SAE") on any of the complication tables as described above or on the AE log identified by the AE verbatim terms containing "vaginal shortening" (case insensitive)
				0 = No, else if subject attended at least one post-operative visit 6 months or after and complication(s) of interest specified above are reported as "Not Evident" across all attended post-operative visits. Subjects with missing responses are included as long as the subject has at least one "Not

				Evident" response (assuming low missing response rate among attended visits). . = Missing, otherwise
Reportable adverse events by system organ class (MedDRA coding)	AE log	Nominal Categorical	surgery through last visit	Through the timepoint of follow-up, based on the systematic collection of open-ended reportable adverse events as reported on the AE log with an onset start date on or after the date of surgical intervention, the adverse events will be coded following the MedDRA dictionary.
				Reportable adverse events are defined in the MOP as follows:
				- During the First Six Weeks Following Surgery: All AEs and SAEs of grade II or higher will be collected.
				- Between Six Weeks and Six Months: All AEs and SAEs that are deaths, require a hospitalization or an emergency room visit, and all AEs or SAEs of grade II or higher that are at least possibly related to the pelvis or surgery, in the opinion of the investigator, will be collected.
				- At All Remaining Visits: Only deaths and AEs or SAEs of grade II or higher that are at least possibly related to the pelvis or surgery, in the opinion of the investigator, will be collected.

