				*Note: Events reported on the AE log corresponding to the following functional efficacy outcomes will be excluded: new or worsening stress urinary incontinence (MedDRA coded preferred term "stress urinary incontinence"), new or worsening urgency urinary incontinence (MedDRA coded preferred term "urge incontinence"), new or worsening fecal incontinence (MedDRA coded preferred term "faecal incontinence"), dyspareunia (MedDRA coded preferred term "dyspareunia"), and new or worsening voiding dysfunction (MedDRA coded preferred term "urinary retention") (case insensitive).
Reportable serious adverse events by system organ class (MedDRA coding)	AE log	Nominal Categorical	surgery through last visit	Through the timepoint of follow-up, based on the systematic collection of open-ended reportable adverse events as reported on the AE log with an onset start date on or after the date of surgical intervention where the

adverse events will be coded following the MedDRA dictionary and classified as a serious adverse event as defined in the MOP as any reportable adverse event that:
- results in death
- is life-threatening (places the subject at immediate risk of death from the event as it occurred)
- results in inpatient hospitalization or prolongation of existing hospitalization
- results in a persistent or significant disability/incapacity
- is another medically important condition - based upon appropriate medical judgment, may jeopardize the subject's health and may require medical or surgical intervention to prevent one of the other outcomes listed in this definition (examples of such events include allergic bronchospasm requiring intensive treatment in the emergency room or at home, blood dyscrasias or convulsions that do not result in inpatient hospitalization, or the development of drug dependency or drug abuse)
- medical or surgical intervention was necessary to preclude permanent impairment of a body function, or prevent permanent damage to a body structure, either situation suspected to be due to the use of a medical product (Devices)
A life-threatening AE is defined as any AE that in the view of the investigator places the study subject at immediate risk of death. It does not include an AE that might have caused death had it occurred in a more severe form.
A disability is defined as a substantial disruption of a person's ability to conduct normal life functions.

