				*Note: Events reported on the AE log corresponding to the following functional efficacy outcomes will be excluded: new or worsening stress urinary incontinence (MedDRA coded preferred term "stress urinary incontinence"), new or worsening urgency urinary incontinence (MedDRA coded preferred term "urge incontinence"), new or worsening fecal incontinence (MedDRA coded preferred term "faecal incontinence"), dyspareunia (MedDRA coded preferred term "dyspareunia"), and new or worsening voiding dysfunction (MedDRA coded preferred term "urinary retention") (case insensitive).
Indicator of death outcome	AE log	Binary	surgery through last visit	Through the timepoint of follow-up, based on the systematic collection of open-ended reportable adverse events as reported on the AE log with an onset start date on or after the date of surgical intervention where the adverse events will be coded following the MedDRA dictionary, the indicator is defined as follows: 1 = Yes, if the outcome of death is reported on the AE log as described above 0 = No, else if subject attended the surgical intervention visit . = Missing, otherwise

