## **10.3** Secondary Safety/Tolerability Outcomes

In general, data for all secondary safety/tolerability outcomes are collected longitudinally across the study on complication tables at each visit and systematic collection of open-ended adverse events reported on the AE log. Secondary safety/tolerability outcomes are generally reported as a binary outcome evaluated in an aggregate fashion (e.g. through 5 years).

Treatment groups will be compared for binary safety outcomes using unadjusted chi-squared tests or Fisher's exact tests for rare events with expected cell counts < 5.. Risk differences with 95% CIs are based on Mantel-Haenszel estimates for the risk difference with Wald-type CIs. For events with expected cell counts < 5, the exact risk difference and 95% CI are obtained by exact methods based on the score statistic based on Chan and Zhang (ref Chan, Zhang 1995). Where specified, Binomial 95% CIs for proportions are based on the exact Clopper-Pearson method (ref Clopper, Pearson). These are the same methods as used for aggregate binary efficacy outcomes.

Maximum dindo score will be analyzed as an ordinal outcome with an unadjusted Mantel-Haenszel chi-squared mean score test with standardized midranks scoring (MODRIDIT option in SAS).

For any continuous or binary safety outcomes measured and analyzed as repeated measures, the same Mixed models as specified for efficacy assessments will be used. Continuous or ordinal safety outcomes assessed at a single timepoint, mean differences, 95% CIs, and *P* values are unadjusted and based on *t* tests for normally distributed continuous outcomes, and *P* values for non-normal continuous outcomes (summarized with medians) are from Wilcoxon Rank Sum tests.

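### SAP 10.2 removes five event types, serious ones included, from the AE and SAE variables, while SAP 10.4, 10.5 and eTables 5 and 6 remove nothing

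*SAP*

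**What the plan says.** SAP 10.2 defines two log-based variables, "Reportable adverse events by system organ class (MedDRA coding") and "Reportable serious adverse events by system organ class (MedDRA coding"). Both run from surgery to last visit, which SAP 4.1 puts at 36 to 60 months. Each ends with the note "Events reported on the AE log corresponding to the following functional efficacy outcomes will be excluded", followed by five preferred terms: stress urinary incontinence, urge incontinence, faecal incontinence, dyspareunia and urinary retention. The wording is the same in both places, and serious events are not exempted.

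The five conditions are counted in SAP 9.3 as secondary efficacy indicators, for example "Indicator of new or worsening fecal incontinence (FI") and "Indicator of new or worsening voiding dysfunction". Each is a single yes/no that turns to yes on either an AE or an SAE response. Each has a timepoint of surgery to 3 years; the dyspareunia indicator, for instance, draws on the AE log and on "specific complications as reported on the coordinator follow-up CRF-13 collected in 6-month intervals through 3 years". For repeated secondary efficacy outcomes, SAP 9.5.1 says that "analyses will include data only collected through 3 years (visits occurring after 3 years are excluded") unless otherwise specified.

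The safety sections read differently. SAP 10.3 says: "Secondary safety/tolerability outcomes are generally reported as a binary outcome evaluated in an aggregate fashion (e.g. through 5 years"). SAP 10.4 plans SAEs by system organ class and preferred term by arm. SAP 10.5 plans the same for all AEs on the AE forms. The display list in SAP 14 has eTable 5 (AEs) and eTable 6 (SAEs) by class and preferred term. None of these three places mentions an exclusion.

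**The concern.** Moving an event from the AE table to an efficacy table is harmless if the second place records what the first would have shown. Here it does not, in two respects. The 9.3 indicators do not separate a serious event from a non-serious one, and they stop at 3 years while the AE and SAE variables run to last visit.

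The SAP also gives two incompatible instructions. A programmer who works from the variable definitions in 10.2 and one who works from 10.4, 10.5 and the display list would produce different SAE tables from the same data.

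The events are not peripheral. Protocol N.2 lists dyspareunia among the mesh risks that every patient is told about. Protocol N.4 counts new or worsening dyspareunia that prevents intercourse as an important complication. SAP 3.2 lists de novo and worsening dyspareunia under safety as well as under function.

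**Working it through.** The plan gives no figure to reproduce. The check is a comparison of definitions, plus one calculation of how much follow-up lies outside the 3-year window.

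**Definitions side by side**

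| Place | Five event types | Seriousness kept | Window |
|---|---|---|---|
| SAP 10.2, reportable AE | removed | not applicable | surgery to last visit |
| SAP 10.2, reportable SAE | removed | yes, for what remains | surgery to last visit |
| SAP 9.3, five indicators | counted | no, AE and SAE pooled | surgery to 3 years |
| SAP 10.4, SAE summary | no exclusion | yes | no 3-year limit |
| SAP 10.5, all AEs | no exclusion | not applicable | no 3-year limit |
| eTables 5 and 6 | no exclusion | yes, in eTable 6 | no 3-year limit |
| SAP 10.2, maximum Dindo | included, type not shown | grade only | to last visit |

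All five excluded terms appear in both notes, and all five matching 9.3 indicators stop at 3 years. The voiding dysfunction definition has one free-text clause that mentions later annual visits, but its timepoint column and its main window are 3 years.

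**Where one event goes if 10.2 is followed**

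- Non-serious, within 3 years: counted in 9.3. Nothing is lost, and double counting is avoided.
- Serious, within 3 years: counted in 9.3 as a plain yes; absent from the SAE table.
- Non-serious, after 3 years: in no AE or occurrence variable.
- Serious, after 3 years: in no AE, SAE or occurrence variable.

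The last two can still raise a woman's maximum Dindo score or set its grade III or higher indicator, without showing the event type. Treated urinary incontinence also enters the retreatment indicator in 9.3, which runs to 60 months. If 10.4 and 10.5 are followed instead, all four cases are in the AE or SAE tables.

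**Follow-up after month 36**

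Inputs: recruitment over 36 months (SAP 6), follow-up until the last participant reaches 36 months with a 60-month maximum (SAP 4.1), and loss of at most 5% per year (SAP 6). Uniform entry is an assumption.

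- Follow-up per woman is min(36 + u, 60), with u uniform on 0 to 36 months. Mean time after month 36 = (24/36) × 12 + (12/36) × 24 = 8 + 8 = 16 months. Mean total = 36 + 16 = 52. Share = 16/52 = 30.8%.
- With 5% loss per year, months observed up to month 36 = 12 × (1 − 0.95³)/(−ln 0.95) = 33.4. Mean total = 46.5, so 13.1 fall after month 36. Share = 28.3%.
- Entry by calendar year can instead be taken from Table 3 of the E-ASPIRe addendum (22%, 35%, 33% and 11% for 10, 9, 8 and 7 years). First surgery is assumed in March 2016, with last surgery in June 2019 and end in June 2022. Mean total is about 53.0 months, with 17.0 after month 36. Share = 17.0/53.0 = 32%.
- The same entry pattern with 5% loss per year gives 47.3 and 14.0 months, a share of about 29.5%.

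The range is therefore 28% to 32% of follow-up time.

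**The case against.** The strongest reply is that the sections on SAEs and AEs (10.4 and 10.5) and the planned eTables list these events by preferred term without exclusion. The two 10.2 variables are labelled by system organ class only and could be a separate summary, and the table shells are in a document that is not public. This stands to the extent that a reader might infer that serious events have been lost from the report. The documents do not show that. They show a contradiction, with a loss only if 10.2 is the text that is followed.

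There is also partial cover. The grade III or higher Dindo indicator is compared by arm to last visit, so severe complications of these types can enter it. Protocol N.5 has all AEs and SAEs summarized for the DSMB by randomized group. Neither puts a serious dyspareunia or retention event, named as such, into the published SAE table.

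A reader might also take the 3-year window of the 9.3 indicators as an error in itself. It is a stated choice: the primary aims run through 3 years, SAP 9.5.1 limits repeated secondary outcomes to 3 years, and later follow-up depends on entry date. What is not explained is the mismatch with the window of the variables from which the events are removed.

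It is tempting to put a number on missed dyspareunia from the 8% de novo rate in protocol Table 10. That series had 115 women, of whom only 13 (11%) had a prior hysterectomy, whereas every ASPIRe participant has had one. In addition, after 6 months the AE log takes only events of grade II or higher that are at least possibly related to the pelvis or surgery. The rate does not transfer, so no count is given.

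Finally, SAP 3.2 item 3.b.v names treatment for voiding dysfunction, fecal incontinence and dyspareunia, and 9.3 derives no variable for these. That does not arise from the exclusion note and depends on CRF content that is not in the documents. It is a separate point.

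**Conclusion.** The SAP contradicts itself on whether five event types belong in the AE and SAE summaries. If the 10.2 notes are followed, the SAE table by arm is incomplete for these types at any time, and events after 3 years are in no AE, SAE or occurrence variable. The period concerned is 28% to 32% of follow-up time, assuming either uniform entry over 36 months or the E-ASPIRe entry pattern, with loss of 0% to 5% per year. This is not a share of events. The documents give no rate for serious events of these types and no basis for a direction between arms. The results affected are descriptive safety results, and the primary analysis is untouched. Leaving non-serious events within 3 years out of the AE variable is reasonable and is not challenged. The point still deserves action: an SAE table should not depend on which section a programmer reads, and the correction is small.

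**What to change.** Issue a dated addendum, labelled post hoc because SAP Version 2 already shows events by arm, applied alike to all arms and described as descriptive:

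1. Delete the exclusion note from the reportable SAE variable, so that every SAE is tabulated by arm.
2. For the reportable AE variable, either delete the note or limit it to non-serious events with onset within 3 years, which 9.3 already counts.
3. State that 10.2, 10.4, 10.5 and eTables 5 and 6 use the same event set.

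Extending the 9.3 indicators to last visit is optional.

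The cost is SAP wording and programming. No new data are needed, since the AE log is already collected and MedDRA coded to last visit.
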